1 PROTOCOL SUMMARY

1.1 Synopsis

Sponsor Name: Cerevel Therapeutics, LLC

Name of Investigational Medicinal Product: Tavapadon

Protocol Title: A Phase 3, Double-Blind, Randomized, Placebo-Controlled, Parallel-Group, 27-Week Trial to Evaluate the Efficacy, Safety, and Tolerability of Two Fixed Doses of Tavapadon in Early Parkinson's Disease (TEMPO-1 Trial)

Short Title: Fixed-Dose Trial in Early Parkinson's Disease

IND Number: 118,647

EudraCT Number: 2019-002949-38

Trial Phase: 3

Indication: Parkinson's disease

Rationale: Tavapadon (PF-06649751, CVL-751) is a partial agonist of the dopamine D1-like receptors (D1Rs), with high specificity for the D1 and D5 receptor subtypes (D1/D5), which is being developed as a treatment for Parkinson's disease (PD). The efficacy, safety, and tolerability of tavapadon in Phase 1b and 2 trials support its potential as the first partial agonist therapy in an important new dopamine receptor-selective mechanism for treatment of PD symptoms. By targeting the D1R subtype, tavapadon aims to improve motor control symptoms while minimizing adverse events (AEs) that may be mechanistically linked to D2/D3 dopamine receptor agonists (notably, dose-limiting hypotension, impulse control disorders, sleep disorders, and, potentially, some forms of hallucinations). This trial is designed to further define and confirm the magnitude of efficacy and the risk/benefit profile of tavapadon over the target dose range of 5 to 15 mg once daily (QD).

Objectives and Endpoints:

The objectives and efficacy, safety, and pharmacokinetic (PK) endpoints of the trial are summarized in [Table 1](#).

Table 1 Objectives and Endpoints

Objectives	Endpoints

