5.9.2. Main Analytical Approach

The change from baseline to each study visit in MDS-UPDRS Part II and III combined score will be summarized by visit and treatment group. A mixed model repeated measures (MMRM) analysis will be used to analyze the data from all post-randomization timepoints up to Week 27 with fixed effect of treatment group, visits, interaction between treatment group and visit, and baseline MAO-B inhibitor use. The baseline value of MDS-UPDRS Part II and III combined score will also be included as a covariate. Subject will be included as a random effect. An unstructured covariance structure will be used for the repeated measures. If the unstructured covariance matrix results in convergence issue, the heterogeneous Toeplitz covariance structure followed by the heterogeneous first-order autoregressive (AR(1)) structure will be used. The Kenward-Roger approximation will be used to estimate the denominator degrees of freedom. The difference between each active dose and placebo at the endpoint visit (Week 26) will be estimated based on the Least Squares Mean (LSMean) difference derived from the MMRM with the associated 95% confidence intervals (CI) and P-values. A Cohen's D value will also be derived as the ratio of the estimated difference to the population standard deviation at each visit estimated from the model (the square root of the diagonal elements of the estimated covariance matrix). The missing values, including missing due to missed visits or early termination due to COVID-19 control measures, are assumed to be missing at random (MAR) in the main MMRM analysis. Sensitivity analyses will be performed to assess the impact of deviation from MAR assumptions on the analysis results. Time curve plots will be presented for both raw Mean (SEM) and LSMean (SE).

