5.14.1. Adverse Events

Adverse events will be mapped to a Medical Dictionary for Regulatory Activities (MedDRA) version 27.0 or higher preferred term and system organ class. If a subject experiences multiple events that map to a single preferred term, the greatest severity and strongest investigator assessment of relation to IMP will be assigned to the preferred term for the appropriate summaries. Events with missing severity or relationship will be classified as outlined in [Section 3.2](#). Missing onset dates will be imputed as previously outlined in [Section 4.1](#) as required to determine treatment-emergent events.

Summaries of treatment-emergent AEs will include any AEs reported beginning with the initiation of study drug on Day 1 through end of reporting period specified in the protocol post the last dose of IMP. The occurrence of TEAEs will be summarized by treatment group using preferred terms, system organ classes, and severity. The TEAEs by subgroup of MAO-B inhibitor use will be summarized by treatment, organ class, and preferred term. Separate summaries of treatment-emergent serious adverse events (TESAEs), TEAEs related to IMP, AESIs (including AEs related to abuse potential and AEs involving medication handling irregularities), events leading to the discontinuation of IMP, and AESIs that did not result in discontinuation of IMP or study will be generated respectively. A summary of AEs by treatment phase and by dose at event onset will also be presented. Adverse events leading to the discontinuation of IMP by preferred term and phase at onset will be prepared. All adverse events reported will be listed for individual subjects showing both verbatim and preferred terms. All adverse events that occurred prior to the initiation of study treatment or after the protocol-specified reporting period post the last dose of IMP will be excluded from the summary tables but will be included in the listings.

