5.14.2. Epworth Sleepiness Scale (ESS)

The ESS individual questions and total score and corresponding changes from baseline will be summarized by treatment group and study visit. The percentage of subjects with sleepy (10 or more) and very sleepy (18 or more) scores will also be summarized. ESS individual question score as well as the total score will be presented in a listing. The ESS total score will also be analyzed using the same method (MMRM analysis) described in [Section 5.9.2](#) to explore any treatment difference in sleepiness. Time curve plot will be presented for LSMean (SE) of change from baseline.

5.14.3. Questionnaire for Impulsive-Compulsive Disorders in Parkinson Disease Rating Scale (QUIP-RS)

The QUIP-RS component scores (Gambling, Sex, Buying, Eating, Hobbyism-Punding, PD Medication Use), total ICD score, and total score and corresponding changes from baseline will be summarized by treatment group and study visit. QUIP-RS individual data will be presented in a listing. The total ICD score will also be analyzed using the same method (MMRM analysis) described in [Section 5.9.2](#) to explore any treatment difference in impulsive-compulsive behaviors. Time curve plots will be presented for LSMean (SE) of change from baseline.

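### SAP 5.14.3 plans no QUIP-RS-based count of subjects with new or worsened impulse control symptoms, and no confidence limit on the incidence of any impulse control harm

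*SAP*

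**What the plan says.** The protocol synopsis names the harms that tavapadon is meant to reduce relative to D2/D3 agonists, among them "dose-limiting hypotension, impulse control disorders, sleep disorders". QUIP-RS is a listed safety endpoint, collected at baseline and at every treatment visit.

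For this scale SAP 5.14.3 plans three things:

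- Descriptive summaries: for the component scores, "total ICD score, and total score and corresponding changes from baseline will be summarized by treatment group and study visit".
- A listing of individual data.
- A model that takes its method from the primary analysis: "The total ICD score will also be analyzed using the same method (MMRM analysis) described in" that part of the SAP. Its stated purpose is "to explore any treatment difference in impulsive-compulsive behaviors". Section 5.9.2 reports differences "derived from the MMRM with the associated 95% confidence intervals (CI) and P-values".

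No cut-off and no number of subjects newly affected is defined. For the Epworth scale, by contrast, SAP 5.14.2 adds subject-level categories: "The percentage of subjects with sleepy (10 or more) and very sleepy (18 or more) scores will also be summarized".

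Impulse control events recorded as AEs fall under SAP 5.14.1: "The occurrence of TEAEs will be summarized by treatment group using preferred terms, system organ classes, and severity". The same section adds rates per 100 person-years. No grouped impulse control term and no interval is described, and SAP 3.2.3.1 does not list impulse control disorder as an AE of special interest.

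**The concern.** An impulse control disorder arises in individuals. Exclusion criterion 5 removes people with a history or current diagnosis of a clinically significant one, so harm in this trial would show as new cases in a minority while most scores stay low. A difference in means spreads those few large rises over the whole arm.

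The interval for the mean does not solve this, because one mean difference fits very different shares: 0.8 points is 10% of subjects rising 8 points or 5% rising 16. So neither the p-value nor the interval says how many subjects may be harmed. A non-significant result on a harm named in the rationale could be given more weight than it can bear. A count improvised from the listing after unblinding would be post hoc.

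**Working it through.** **Plan's own figures.** There are none for QUIP-RS: no SD, shift, event rate, margin or power. The SAP's primary sample size serves only to fix the number evaluable. With difference 4, SD 9, two-sided alpha 0.025 and 90% power, n = 2 x (2.2414 + 1.2816)^2 x 81/16 = 125.7, so 126 evaluable. Then 126/0.73 = 172.6, so 173, against 174 stated. Conversely, 174 x 0.73 = 127 per arm.

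**Assumptions, none from the documents.** Share affected is 0% on placebo and p = 5% or 10% on active. An affected subject rises S = 8 or 16 points, which is half or all of the 0-16 range that SAP 3.2.1 gives for one disorder. SD of change in the other subjects is 1 to 7. Two-sided alpha is 0.05. The items that make up the total ICD score are not defined in the SAP.

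**Mean test.** The mean shift is d = pS. The pooled SD is s = sqrt(SD^2 + S^2 p(1-p)/2), SE = s x sqrt(2/127), and power is about Phi(d/SE - 1.96).

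- p = 5%, S = 8, SD 2: d = 0.4, s = sqrt(4 + 1.52) = 2.35, SE = 0.295, power = Phi(-0.60) = 27%, missed 73%.
- p = 5%, S = 16, SD 3: d = 0.8, s = sqrt(9 + 6.08) = 3.88, SE = 0.487, power = Phi(-0.32) = 37.5%, missed about 63%.
- p = 5%, S = 8, SD 7: d = 0.4, s = sqrt(49 + 1.52) = 7.11, SE = 0.892, power = Phi(-1.51) = 7%, missed 93%.

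Simulation of the t-test agrees within a point or two, except at small SD with large shifts, where the approximation understates power and simulation is used. Approximate miss rates at 127 per arm:

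| Affected on active | SD 1-2 | SD 3-7 |
|---|---|---|
| 5% | 28-73% | 63-93% |
| 10% | 1-30% | 18-85% |

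With 174 per arm the 5% row becomes 13-67% and 53-92%, so the conclusion does not hang on using 127.

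**Interval for the mean.** The half-width is 1.96 x SD x sqrt(2/127) = 0.246 x SD, ignoring the extra spread from cases: 0.74 at SD 3, 1.23 at SD 5, 1.72 at SD 7. At SD 5 or 7, a result centred on zero would exclude neither 0.4 nor 0.8.

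**Test on shares (Fisher exact).**

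| Placebo v active | 127 per arm | 174 per arm |
|---|---|---|
| 0% v 5% | 61% | 87% |
| 2% v 7% | 36% | 53% |
| 2% v 5% | not tabulated | 22% |

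**Interval on shares, 174 per arm.** With 0 cases the two-sided 95% upper limit is 1 - 0.025^(1/174) = 2.1%. For 3 v 3 cases the risk difference is 0, with Newcombe interval -3.4 to +3.4 points. For 9 v 3 it is 6/174 = 3.4 points, -0.6 to +8.0.

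**The case against.** The strongest reply is that the plan is broader than a mean. All TEAEs are tabulated by arm and expressed per person-year. AEs leading to discontinuation are of special interest and get their own summary and narratives. The SAP's descriptive statistics include quartiles and the maximum, so a single large rise in a component score would show there and in the listing. AE capture is not limited to what subjects volunteer: the schedule footnote includes events observed by staff, caregivers may report, and a clinically significant abnormal safety assessment meets the AE definition. All of this stands. A reader might infer that no incidence of any kind is planned; the documents do not support that. What remains is that AE incidence depends on recognition and reporting, is split across preferred terms, and carries no interval.

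A second reply concerns the numbers. If most subjects sit near zero, the SD may be small, and at SD 1-2 a rise in 10% of subjects is usually found. With SD 1 and a 16-point rise in 5%, the mean test (about 28% missed) even beats Fisher's test at the same 127 per arm (39% missed). This also stands, so it cannot be said that the mean test would usually miss a relevant harm.

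Third, any cut-off has unknown specificity. If 10% of placebo subjects met it, Fisher power for 10% v 15% at 174 per arm is 24%. That is a reason to rely on the interval and to choose the cut-off with care.

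Finally, the model is labelled exploratory, the protocol plans only descriptive statistics for QUIP-RS, and the confirmatory hypotheses H1-H6 do not include this harm. A reader might infer that the sponsor intends to claim absence of risk from a null mean. Nothing in the documents says so. With no D2/D3 agonist arm, no QUIP-RS analysis here could test an advantage over that class.

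**Conclusion.** The gap is real but limited. QUIP-RS yields no planned count of subjects newly affected, and no incidence of impulse control harm is given a confidence limit. The one between-group comparison directed at this harm is an exploratory test of a mean.

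Under the assumed values, a null mean is weak evidence against harm in about 5% of subjects: missed 28-73% of the time at SD 1-2 and 63-93% at SD 3-7. A large rise in 10% could well be detected. All of these figures rest on an SD, shift and event rate that the documents do not supply. A p-value on shares would not settle the matter either; the benefit is an explicit upper limit on the excess share affected. This is a cheap improvement and does not touch the primary or key secondary analyses.

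**What to change.** Add to SAP 5.14.3, in the FAS by arm, the number and percentage of subjects with a new ICD signal at any post-baseline visit, overall and for each of the four ICDs (gambling, buying, eating, sexual behavior). The sponsor fixes the cut-off before unblinding. One example, no more than that, is any item of the disorder scored 3 or 4 when all its items were 2 or below at baseline, on the response scale in SAP 3.2.1.

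Report each dose-minus-placebo risk difference with a 95% interval. Keep the MMRM as exploratory, and state that a non-significant mean difference will not be taken as absence of ICD risk.

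Cost: SAP wording and one more table, from data already collected at every treatment visit. Downsides: a cut-off of uncertain specificity and an interval that may be wide.

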5.14.4. Non-IMP Medications and Non-Drug Therapy/Procedures

The use of non-IMP medications will be coded using the World Health Organization (WHO) drug dictionary (WHODrug) (Version: Global B3 September 2019 or later). Concomitant medications, with start date on or after the date of the first IMP through the last IMP dose date, will be summarized by treatment group, frequency of drug classification, and generic drug name. Medications with start date after the last dose of IMP through the end of protocol-defined reporting period, will also be summarized. Prior medications use will be similarly summarized. All prior, concomitant, and post IMP medications will be presented in a data listing.

The use of non-drug therapy/procedures will be coded using MedDRA Version 27.0 or higher. Concomitant and post-IMP non-drug therapy/procedures will be summarized by treatment group, frequency of system organ class and preferred term. All non-drug therapy/procedures will be presented in a data listing.

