10.	Subjects who are treatment naïve or have a history of prior incidental treatment with dopaminergic agents (including L-Dopa and dopamine receptor agonist medications) for <3 months in total but not within 2 months of the Baseline Visit. Prior and concurrent use of MAO-B inhibitors is permitted if use was initiated >90 days before the Baseline Visit and the dosage will remain stable for the duration of the trial (ie, no change in the MAO-B inhibitor dose is permitted during the trial).
11.	Subjects who are willing and able to refrain from any PD medications that are not permitted by the protocol (including dopaminergic agents) throughout participation in the trial.

Abbreviations: ICF = informed consent form, IMP = investigational medicinal product, L-Dopa = levodopa, MAO-B = monoamine oxidase B, MDS-UPDRS = Movement Disorder Society-Unified Parkinson's Disease Rating Scale, PD = Parkinson's disease.

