6.5.3 Prohibited Medications During the Trial

The concomitant medications that are prohibited during the trial are listed in [Table 7](#).

The medical monitor should be contacted regarding the appropriateness of a subject's continued participation in the trial in the event that initiation of therapy with a prohibited

concomitant medication is deemed necessary, in the investigator's opinion, for the treatment of a treatment-emergent adverse event (TEAE).

Table 7 List of Medications Prohibited During the Trial

	Medication
1.	Sedatives, hypnotics, antidepressants, and anxiolytics (unless dose has been stable for >90 days before the Baseline Visit and will remain stable for the duration of the treatment phase) Note: Short-term use of lorazepam (up to 4 mg/day), or its equivalent, for TEAEs of anxiety or insomnia may be permitted following consultation with and approval by the medical monitor, but may not be taken within 12 hours prior to efficacy assessments during clinic visits. Use should be discontinued upon TEAE resolution.
2.	Atypical antipsychotics
3.	COMT inhibitors
4.	Dopamine antagonists, such as neuroleptics/antipsychotics (eg, phenothiazines, butyrophenones, thioxanthenes), including: 
 Haloperidol Trimethobenzamide or domperidone (for nausea/vomiting) Metoclopramide Quetiapine (for insomnia)
5.	Droxidopa
6.	Istradefylline
7.	L-Dopa or dopamine agonists (including levodopa inhalation powder or apomorphine)
8.	Anticholinergic drugs Note: Short-term use of scopolamine for TEAEs of nausea may be permitted following consultation with and approval by the medical monitor, but may not be taken within 12 hours prior to efficacy assessments during clinic visits. Use should be discontinued upon TEAE resolution.
9.	Methyldopa
10.	Amantadine
11.	Moderate or strong CYP3A4 inducers ^a (refer to Section 10.6 [Appendix 6] for examples)
12.	Moderate or strong CYP3A4 inhibitors ^a (refer to Section 10.6 [Appendix 6] for examples)
13.	Mood stabilizers 
 Anticonvulsants Lithium Note: Use of certain anticonvulsants (eg, pregabalin) for medical reasons unrelated to seizures or psychiatric mood stabilization may be allowed after discussion with and approval by the medical monitor.
14.	Nonselective MAO inhibitors

Table 7 List of Medications Prohibited During the Trial

	Medication

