3.2.8. Prior Medications, Concomitant Medications and Medications Taken Post Last Dose of IMP

Prior medications are those medications taken prior and ended prior to the initiation of IMP. These medications will be captured in the CONCOMITANT MEDICATIONS eCRF.

Concomitant medications are those medications taken on or after the initiation of IMP. These medications include those medications started before the initiation of IMP and continuing post Day 1. Medications that start after the last dose of IMP until the end of protocol-specified reporting period will be classified as taken post last dose and will not be considered concomitant. These medications will be recorded in the eCRF. The investigator will record all medications and therapies (including vaccines, over-the-counter or prescription medicines, vitamins, and/or herbal supplements) that are used by the subject from 30 days before the informed consent form (ICF) is signed through the end of the Safety Follow-up Period (Week 31 or early termination). The investigator will also record all medications and therapies taken or received by a subject for treatment of an AE or that cause an AE through Week 31 or early termination.

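### SAP 5.14.4 contradicts SAP 3.2.8: read literally, a drug already in use at Day 1 and continued falls in none of the three medication summary tables

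*SAP*

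**What the plan says.** SAP 3.2.8 sets the definitions. "Prior medications are those medications taken prior and ended prior to the initiation of IMP". Concomitant medications are those taken once IMP has begun, and the section removes any doubt about earlier starts: "These medications include those medications started before the initiation of IMP and continuing post Day 1". Drugs begun after the last dose form a third class and are not concomitant.

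SAP 5.14.4 specifies the tables. The concomitant summary, by treatment group, drug class and generic name, covers "Concomitant medications, with start date on or after the date of the first IMP through the last IMP dose date". For the third class, "Medications with start date after the last dose of IMP through the end of protocol-defined reporting period, will also be summarized". For the first, "Prior medications use will be similarly summarized", with no date rule of its own, so the 3.2.8 definition of prior applies. The section also promises a listing of all medications.

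The protocol describes the background drugs. Inclusion criterion 10 (Protocol 5.1) states that "Prior and concurrent use of MAO-B inhibitors is permitted if use was initiated >90 days before the Baseline Visit", and that "no change in the MAO-B inhibitor dose is permitted during the trial". Table 7 (Protocol 6.5.3) lists antidepressants, anxiolytics, sedatives and hypnotics as prohibited, "unless dose has been stable for >90 days before the Baseline Visit and will remain stable for the duration of the treatment phase".

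**The concern.** The two SAP sections use the same term with different contents. Section 3.2.8 asks whether the drug was taken during treatment; 5.14.4 asks whether it was started during treatment. Drugs that pass the first test and fail the second are those a patient was already on at randomization, which is what readers usually look for in a concomitant-medication table.

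At stake is the by-arm description of background therapy. The SAP compares daytime sleepiness between arms with a repeated-measures model (5.14.2) and tabulates blood pressure, heart rate and orthostatic outliers by arm (5.14.6.1). A reader of those results would want to know how many subjects in each arm were on long-standing sedatives, antidepressants or other chronic drugs. A table labelled concomitant that holds only newly started drugs would understate that use without saying so.

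**Working it through.** No sample size, power or error rate is involved, and the plan gives no figure to reproduce. The check is a classification: take each possible pattern of start and stop dates and apply the written rules.

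**Rules**
- Prior: stopped before the first dose (3.2.8, used in 5.14.4).
- Concomitant: start date between the first and last dose dates, inclusive (5.14.4).
- Post-IMP: start date after the last dose (5.14.4).
- Day 1 is the date of first dose (4.1.2).

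| Pattern | Prior | Concomitant (5.14.4) | Post-IMP | Tables as written | Class under 3.2.8 |
|---|---|---|---|---|---|
| A. Started and stopped before Day 1 | yes | no | no | 1 | prior |
| B. Started from Day 1 to last dose | no | yes | no | 1 | concomitant |
| C. Started after last dose | no | no | yes | 1 | post-IMP |
| D. Started before Day 1, still taken on or after Day 1 | no | no | no | **0** | concomitant |

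Pattern D fails each rule for a separate reason: it had not stopped, it started too early for the concomitant table, and its start does not follow the last dose. Under 3.2.8 it belongs to exactly one class.

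**Which drugs are in pattern D**
- *MAO-B inhibitors.* Criterion 10 requires a start more than 90 days before the Baseline Visit, and Protocol 4.1.2 places the first dose at that visit. A permitted concurrent MAO-B inhibitor therefore starts more than 90 days before Day 1 and continues past it. Because its dose may not change, no new on-treatment record is expected to bring it back into the table. One stopped before the first dose is pattern A and is counted as prior.
- *Sedatives, hypnotics, antidepressants, anxiolytics.* Those allowed through the stable-dose exception in Table 7 were also in use more than 90 days before Baseline and continue.
- *Other chronic drugs* permitted in this population aged 40 to 80 follow the same pattern.

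**Possible exception.** SAP 4.1.15 imputes incomplete event start dates. If it is applied to medications, a wholly missing start date becomes Day 1. So does a start date with only the year known, when that year is the year of first dose. For drugs other than MAO-B inhibitors, so can a start date with only month and year known, when these match the month and year of first dose. Such records would move from D to B and enter the concomitant table.

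**What does not depend on the 5.14.4 table**
- MAO-B inhibitor use at baseline is tabulated for the ITT population (5.6).
- Actual MAO-B status enters the efficacy models, including for the 15 subjects randomized in the wrong stratum (5.5), and defines a subgroup (5.9.4, extended in 5.10.1.3 and 5.10.2.3).
- Treatment-emergent adverse events are summarized by MAO-B use and treatment (5.14.1).
- The prohibited Parkinson's medications that trigger censoring have their own date and duration rule (5.9.1).
- Every medication is listed (5.14.4).

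**The case against.** The best defence is that 5.14.4 uses a term already defined correctly in 3.2.8, and that its date clause is loose wording meant only to separate on-treatment drugs from those begun after the last dose, which the next sentence covers. On that reading no drug is lost. It is a fair reading, and it is why the point is a contradiction between two sections and not a settled decision to drop background drugs. It does not dispose of the problem. The clause is an explicit start-date rule, the following sentence applies a parallel one, and the SAP does not say which section governs. A programmer could apply it literally and lose pattern D, put those drugs under prior against 3.2.8, or ignore it and follow 3.2.8. The three choices give different tables. The independent programming promised in 9.4 would not by itself show which was intended.

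A second objection stands in full. A reader might infer that the report would show no background MAO-B inhibitor use at all, or that the interpretation of safety by arm would be wrong. The documents do not support either: the other places where MAO-B use is reported, including adverse events by MAO-B use, do not draw on this table. For that class, the loss is the by-arm count by drug class and generic name. For stable sedatives, antidepressants and other chronic drugs the loss is larger in kind, since the SAP specifies no other summary of them, but they remain in the listing.

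**Conclusion.** The contradiction is real, and 5.14.4 is wrong as written. Followed literally, it places a drug ongoing at Day 1 in 0 of 3 summary tables, where 3.2.8 would place it in one. This rests on two assumptions: that the clause is programmed as it reads, and that start dates are known or are not imputed to Day 1.

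A reader might also infer that all permitted MAO-B users, without exception, drop out of the tables. That goes too far: it holds for concurrent users, subject to the imputation exception, and not for those who stopped before the first dose. The documents give no count of subjects on background drugs, so the understatement cannot be put as a number of subjects.

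The effect is limited to the descriptive medication tables. No efficacy estimate, test or error rate changes, and no adverse-event count depends on them.

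**What to change.** In SAP 5.14.4, delete the start-date clause for concomitant medications and refer to 3.2.8: the table covers any medication taken at any time from first through last dose of IMP, including those begun before Day 1 and continued. Leave the prior and post-IMP rules as they are. Each of the four date patterns then falls in exactly one table, and an ongoing drug whose start date is imputed to Day 1 is classed the same way with or without imputation.

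If the sponsor also wants to show drugs newly started on treatment, that can be a separately labelled subset.

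The cost is one SAP sentence and the matching selection condition in the table program. No new data are needed and no inference changes. It should be made before database lock.
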